 - Sensitivity of Avantect test for detecting PC – number of individuals in the intervention arm with one or more Avantect “detected” test results and PC divided by the number of individuals in the intervention arm with PC.
 - Specificity of Avantect test for ruling out PC – number of individuals in the intervention arm with no Avantect “detected” test results, at least one Avantect “not detected” test result and no diagnosis of PC divided by the number of individuals in the intervention arm with no diagnosis of PC.
 - Resectability rate – number of individuals with PC deemed resectable by the study multidisciplinary team (MDT) divided by the number of PCs.

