9.2 SAMPLE SIZE

Upon conclusion of the pilot, further recruitment to the study will occur with a planned interim analysis for futility and efficacy. Participants in the pilot study will continue to have their data analysed. The planned interim analysis is referred to as ‘stage 1’ analysis for convenience. The final analysis is referred to as ‘stage 2’ analysis. In each stage, there are three co-primary endpoints:

1. sensitivity (of the Avantect test),
2. specificity (of the Avantect test) and

3. resectability of diagnosed PCs

In the stage 1 interim analysis, these endpoints will be assessed within the intervention arm, as more information will be available on the diagnostic status of this group. In the stage 2 final analysis, the sensitivity and specificity of the test will be estimated within the intervention arm, whereas resectability will be compared between the arms.

The anticipated prevalence of a pancreatic cancer diagnosis within 3-years of follow-up within this population is 1%³. Conservative estimates place the anticipated sensitivity of the Avantect test at 65% sensitivity and 95% specificity in the detection of PC. Under usual care in the UK, 10-20%^{13,14} of pancreatic cancer patients receive surgery with curative intent due to the majority (80%) presenting at Stage III or Stage IV¹⁵. Data from the CAPS cohort¹⁶ in the US has demonstrated that it is possible to reduce the proportion of patients presenting with late stage disease if surveillance testing is conducted on at-risk subgroups, thus improving the availability of curative resection as a treatment strategy. It is hoped that the Avantect test can improve the resectability of pancreatic cancers from a rate of 14% in usual care to 40% in the intervention arm (just over a 2.5-fold increase).

With three co-primary endpoints, each endpoint must be reached for an overall successful result. To achieve an overall power of 90%, the power for each endpoint should be $90\%^{(1/3)} = 96.5\%$. Following guidance from Korevaar and colleagues¹⁷, the analysis will consist of a one-sided test at an cumulative alpha of 0.05 at the final analysis. Because there is an interim analysis at stage 1 for efficacy and futility, the one-sided significance level changes at the interim and final analysis.

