Two of the three co-primaries are metrics of test accuracy. In practice test results will not be available for all participants due to machine failure, insufficient blood sample quality, shipping or processing, or participants being unable to provide a blood sample. To reduce the number of participants where no test results are available, three collection time points are included. In the case where a blood draw did not occur or the sample was not analysable following a scheduled visit, a repeat blood draw will be arranged. The expected proportion of participants who are expected to not have a single Avantect result is 2.5%.

Using the PropTestPower function in the R package EnvStats, it was determined that 73 individuals with pancreatic cancer are required in each arm to detect a change of resectability from 14% in usual care to 40% in the intervention arm. At the stage 2 final analysis, allowing for interim analysis, the overall power would be 96.5%. Allowing for 2.5% loss to arrive at the Per Protocol population (see section 9.4), this increases to 75 cases per arm (150 total), which at an event rate of 1% leads to a recruitment target of 7,500 per arm (15,000 total). As only samples from the intervention arm are to

be tested for the purpose of the analysis, with an anticipated test sensitivity of 65% and specificity of 95%, this leads to the following confusion matrix in the intervention per protocol group (7,312):

		Diagnostic status	
		Has PC diagnosis	Does not have PC diagnosis
Avantect test result	Detected	48	362
	Not detected	25	6,877

With 73 cases of pancreatic cancer of which $48/73 = 65\%$ were detected by the Avantect test, this would be sufficient to rule out a sensitivity lower than 42 % in the stage 2 final analysis at 96.5% power. On discussion with the FDA, a specificity of 92% would be considered acceptable within this clinical context. With 6,877 individuals without a pancreatic cancer diagnosis of which $6,877/7,239 = 95\%$ are expected to be detected by the Avantect test, more than 99% power is achieved to rule out a specificity lower than 92%.

Definition of ‘promising result’ in study stage 1 to guide progression to study stage 2

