At the stage 1 interim analysis, co-primaries will be considered ‘futile’, ‘promising’ or ‘efficacious’ according to the following table:

	Expected proportion	Futility threshold at stage 1	Promising result range at stage 1	Efficacy threshold at stage 1
Sensitivity	65%	<46.5%	46.5% to 63.1%	>63.1%
Specificity	95%	<92.0%	92.0% to 94.9%	>94.9%
Resectability	40%	<21.0%	21.0% to 38.1%	>38.1%

At the stage 2 final analysis, the sensitivity co-primary will be considered successful if a sensitivity of 49% can be ruled out with a one-sided p-value of 0.03 among participants in the intervention arm. Specificity will be considered successful if a specificity of 92% can be ruled out with a one-sided p-value of 0.03 among participants in the intervention arm. Resectability will be considered successful if the resectability rate in the intervention arm is higher than the rate in the control arm at a one-sided p-value of 0.03.

Secondary outcomes, in order of importance, are defined as follows, which all are calculated with a minimum of 90% power:

Stage shift - The analysis will be conducted by comparing the proportion of PC cases diagnosed at stage I/II vs III/IV between the intervention and control arms. A proportion of 60% (44/73 PCs) is expected in the intervention arm versus 35% (26/73 PCs) in the control arm, which provides 90% power at a one-sided alpha of 0.05. Stage shift will be considered successful if the proportion in the intervention arm is higher than the rate in the control arm at a one-sided p-value of 0.05.

PPV in detecting PC - The analysis will be conducted within the intervention arm. With a sample size of 7,500, PC prevalence of 1%, and 2.5% lost from the per protocol population, there will be an expected 410 individuals with an Avantect “detected - abnormal” result. 11.6% (48/410) are expected to have a PC. PPV will be considered successful if a null PPV of 5% can be ruled out at a one-sided p-value of 0.05.

NPV in ruling out PC - The analysis will be conducted within the intervention arm with a sample size of 7,500, PC prevalence of 1%, and 2.5% lost from the per protocol population, will be an expected 6,902 individuals without an Avantect “detected - abnormal” result. 99.6% (6,877/6,902) are expected to not have a diagnosis of PC. NPV will be considered successful if a null NPV of 99% can be ruled out at a one-sided p-value of 0.05.

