Resection rate of PC. The analysis will be conducted by comparing resection between the intervention and control arms. With a sample size of 15,000, PC prevalence of 1%, and 2.5% lost to follow-up, there will be an expected 73 cases of PC in each arm. It is assumed that 5% of those deemed resectable will not undergo resection, for an expected rate of 38% (28/73) in the Intervention arm versus 13% (9/73) in the control arm. Resection rate will be considered successful if the proportion in the intervention arm is higher than the rate in the control arm at a one-sided p-value of 0.05.

For analyses of exploratory outcomes, the following applies:

Time-to-event outcomes (time to PC diagnosis and overall survival) will be analysed using a Cox regression model to determine the hazard ratio (and 95% confidence interval) between groups. This will be supported by a Kaplan-Meier plot for each group, median survival (and 95% confidence intervals), and estimates of 3-year survival (T0-T3) (alongside the difference in proportions and corresponding 95% confidence interval). The 6-item STAI will be analysed using a t-test or non-parametric suitable alternative if data are not normally distributed. Performance characteristics for high-grade neoplasia include sensitivity, specificity, PPV and NPV. They will be analysed as described

SAFE-D Clinical Performance Study Protocol Version 4, IRAS Ref: 326332 31-JUL-2025 Page 49 of 68

above, when high-grade neoplasia is also considered as Disease Positive, and when high-grade neoplasia alone (with the exclusion of pancreatic cancer) is considered as Disease Positive. Two-sided p-values will be presented for exploratory outcomes.

Unless otherwise stated, continuous data will be presented as means and standard deviations and analysed using a linear regression modelling framework. If data are skewed, medians and ranges will be presented. To analyse skewed data we will attempt to find a suitable transformation to allow a linear modelling approach. If this is not possible, we will explore whether another suitable parametric distribution fits the data. If not, a non-parametric approach, such as quantile regression, will be used. Binary data will be reported in terms of odds ratios and analysed using logistic regression modelling, unless otherwise stated.

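### Sections 9.2 and 9.4 assume different early-stage shares under usual care (about 20% and 35%); if 35% is right and resectability follows stage, resectability power is about 61-64%, not 96.5%

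*Protocol*

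**What the plan says.** Section 2.2 defines the resectability co-primary as "number of individuals with PC deemed resectable by the study multidisciplinary team (MDT) divided by the number of PCs". As background, section 9.2 gives a usual-care range of 10-20% and says that this share "of pancreatic cancer patients receive surgery with curative intent due to the majority (80%) presenting at Stage III or Stage IV". The stated aim is to "improve the resectability of pancreatic cancers from a rate of 14% in usual care to 40% in the intervention arm". Section 9.2 bases its case count on that difference: "73 individuals with pancreatic cancer are required in each arm to detect a change of resectability from 14% in usual care". It puts the power of this comparison at 96.5%. All three co-primaries must succeed, for an overall power of 90%.

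Section 9.4 sets the assumption for the stage-shift endpoint, the share of cancers at stage I/II: "A proportion of 60% (44/73 PCs) is expected in the intervention arm versus 35% (26/73 PCs) in the control arm". It reports 90% power at one-sided 0.05. For the separate resection endpoint it says: "It is assumed that 5% of those deemed resectable will not undergo resection". This turns 40% and 14% into 38% and 13%.

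**The concern.** Both sections describe patients diagnosed under usual care, and the control arm receives usual care. Section 9.2 implies about 20% stage I/II in that setting; section 9.4 expects 35% in the trial's control arm. Nothing in the protocol explains the difference. Section 9.2 itself attributes the low surgery rate to late stage at presentation, so a higher early-stage share should, on the plan's own logic, come with a higher resectable share. The control resectability rate nevertheless stays at the level that accompanies the 20% mix.

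The resectability comparison gives the 73 cancers per arm and hence the 15,000 participants. If the true control rate is well above 14%, the co-primary that drives the sample size has much less power than stated. Because success needs all three co-primaries, overall power cannot exceed the power for resectability.

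**Working it through.** **Inputs.** From 9.2: control resectability 14%, intervention 40%, 73 cancers per arm, usual-care surgery 10-20%, and 80% at stage III/IV, so 100% - 80% = 20% at stage I/II. From 9.4: stage I/II 35% (control) and 60% (intervention), and final one-sided significance level 0.03 for resectability.

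**Formula.** Two-proportion test with pooled variance under the null: power = Φ[(p1 - p0 - z·s0)/s1], where s0 = √(2p̄(1-p̄)/73), s1 = √((p0(1-p0) + p1(1-p1))/73), p̄ is the mean of p0 and p1, and z = 1.881 at one-sided 0.03.

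**Step 1: the plan's own figure.** For 14% v 40%: p̄ = 0.27, s0 = 0.0735, s1 = 0.0703. (0.26 - 1.881 × 0.0735)/0.0703 = 1.73, so power is 95.8%. A binomial simulation gives 96.2%. The stated 96.5% is reproduced to within a point.

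**Step 2: resectable share per stage I/II cancer.**

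| Setting | Resectable | Stage I/II | Ratio |
|---|---|---|---|
| Usual care (9.2) | 14% | 20% | 0.70 |
| Intervention arm | 40% | 60% | 0.67 |
| Control arm (9.4 stage mix) | 14% | 35% | 0.40 |

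The first two agree and the third does not.

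**Step 3: control rate if 35% is right and the ratio holds.** 0.667 × 35% = 23.3%; 0.70 × 35% = 24.5%. Applied to the intervention arm, 0.70 gives 0.70 × 60% = 42%.

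**Step 4: power at 73 per arm, one-sided 0.03.**

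| Control v intervention | Basis | Power |
|---|---|---|
| 14% v 40% | as planned | 95.8% |
| 20% v 40% | top of the cited 10-20% range, no scaling | 78.1% |
| 23.3% v 40% | ratio 0.67 in both arms | about 61% |
| 24.5% v 42% | ratio 0.70 in both arms | 64.4% |
| 24.5% v 40% | ratio 0.70 in the control arm only | 54.9% |

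For 23.3% v 40%: s0 = 0.0770, s1 = 0.0758, (0.1667 - 1.881 × 0.0770)/0.0758 = 0.29, so 61%. Simulation of the last three rows gives 62.4%, 65.2% and 55.7%.

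**Step 5: dependence on the significance level.** Section 9.4 also gives a 98.5% one-sided interval (0.015) and a cumulative alpha of 0.025; section 9.2 gives a cumulative alpha of 0.05. With both arms scaled, power is 70-73% at 0.05, 58-61% at 0.025 and 50-53% at 0.015. None of these levels restores 96.5%.

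**Step 6: the other resolution.** If 20% is the right early-stage share, the stage-shift comparison is 20% v 60%, not 35% v 60%. At one-sided 0.05 the same formula gives 92% for 35% v 60% (89.5% with continuity correction, matching the stated 90%) and above 99.9% for 20% v 60%.

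**The case against.** The strongest reply is that stage I/II is not the same as resectable. Table 1 in section 7.9.4 classifies resectability by tissue planes, vessel involvement and metastasis, with a separate borderline category. Clinically detected early-stage cancers could be resectable less often than test-detected ones, and a ratio of 0.40 in the control arm is not impossible. This stands: the protocol states no constant ratio, so the power loss is conditional. It does not remove the conflict. A ratio of 0.50 gives 0.50 × 35% = 17.5% and 88% power; 0.60 gives 21% and 73%. Only a ratio near 0.40 keeps the stated power, and the protocol does not argue for one.

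Three stronger readings are tempting but unsupported.

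- A reader might infer that the 14% counts operations rather than resectable cancers, because the only usual-care support near it is a surgery rate. The plan calls it resectability, derives a separate 13% for resection, and does not show the source of 14%. Even if it were surgery, 14%/0.95 = 14.7%, with power still about 95%.
- A reader might multiply the reduced power by 96.5% twice to obtain a new overall power. Section 9.2 states more than 99% for specificity, and sensitivity and intervention-arm resectability come from the same cancers, so an independence product is unsafe. Only the upper bound is secure.
- A reader might infer a raised risk of a false efficacy stop at Stage 1. Section 9.2 stops for efficacy only if all endpoints are efficacious and sends mixed results to the oversight committees. The final resectability comparison uses a concurrent randomised control arm.

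That concurrent control also means a wrong planning rate affects power, not the validity of the final test.

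**Conclusion.** The point holds as an unreconciled pair of planning assumptions. Sections 9.2 and 9.4 cannot both describe the control arm without an explanation that the protocol does not give, and one of the two power statements needs correcting whichever way this is settled.

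- If 35% is right and the resectable share of stage I/II cancers is about 0.67-0.70 in both arms, control resectability is 23-25% and power at one-sided 0.03 is about 61-64%. It is 55% if the control rate is 24.5% and the intervention rate stays at 40%.
- If 20% is right, the 14% and its power can stand, and the stage-shift control rate is the wrong figure.

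The constant share is an assumption of this check and is not stated in the protocol. Without it, the cited 10-20% range alone takes power down to about 78% at its upper end, so a single 96.5% conveys more certainty than the plan's inputs support.

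**What to change.** In 9.2 and 9.4, adopt one control-arm stage distribution and derive both the stage-shift and the resectability control rates from it. If the two are meant to differ, explain why the resectable share of early-stage cancers is lower in the control arm. State the control resectability rate on the endpoint's own definition, cancers deemed resectable by the study MDT, and give its source.

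Replace the single 96.5% and 90% with a range over control rates of 14% to 25%. At 73 per arm, 40% in the intervention arm and one-sided 0.03, resectability power runs from about 96% to about 52%, and overall power can be no higher than that. Recheck the Stage 1 resectability thresholds (21.0% and 38.1%) against the reconciled rate, since that look has no control arm of its own.

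The cost is protocol wording, recalculated figures and a less favourable stated power. No change in enrolment is proposed.

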1.2 RATIONALE (INCL. RISK-TO-BENEFIT) FOR IVD MEDICAL DEVICE UNDER INVESTIGATION

Research⁵ shows that 5-hydroxymethylation changes in plasma-derived cell-free DNA (cfDNA) can be used for early detection of PC. 5-hydroxymethylcytosine (5hmC) is a stable epigenetic mark that arises as the first step of active demethylation of methylated-cytosine base in DNA by ten-eleven translocation enzymes, marking regions of active transcription and gene regulation⁶. Based on the technology developed⁶, the Avantect blood-based test utilises 5hmC, fragmentation and copy number variation (CNV)-based biomarkers from cfDNA whose measures are associated with the detection of PC. The test employs state-of-the-art machine learning stacked ensemble modelling that combines multiple feature sets to predict the presence of PC using 5hmC-based epigenomic and genomic signatures in cfDNA. The ensemble model was trained and rigorously tested using 25 iterations of 10-fold outer cross validation. Specifically, for each fold in the outer folds, a model was trained on the in-fold data using further 10-fold cross validation and tested on the remaining out-of-fold data. The model parameters and classification score threshold was optimised during inner fold training. A classification score threshold that represented the 98% specificity in the training set was chosen. The model was validated in an independent cohort of 2,150 participants of which 2,048 were non-cancers and 102 with PC. The performance of PC detection was at 66.7% sensitivity and 96.9% specificity with an early-stage PC (Stage I and II) sensitivity of 68.3%.

ClearNote Health feasibility data also suggests that the Avantect test may detect a subset of neoplastic cysts, including intraductal papillary mucinous neoplasms (IPMNs) and pancreatic intraepithelial neoplasms (PanINs). IPMNs of the pancreas and PanINs are PC precursors. Just as colon polyps can develop into colon cancer if left untreated, some IPMNs have the potential to become malignant, so it is important to diagnose and manage them early and appropriately before they develop into an invasive cancer.

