An analysis for futility and efficacy will be conducted once 3,200 individuals randomised to the intervention arm have returned for the third blood-draw (T2) in order to obtain cancer outcome data from the cancer registry. This amounts to 43.8 % of the total information accrual in the intervention arm, accounting for 2.5% not qualifying for the Per Protocol population (see 9.4; $3,200/7,312$). All individuals with one or more Avantect “detected” test results will be included as positive predictions. Individuals whose Avantect test results are all “not detected” will be included as negative predictions. Based on a cumulative one-sided alpha of 0.05 and 96.5% power for the three co-primary outcomes, the futility and efficacy thresholds at stage 1 interim analysis are detailed in the table below. If all study endpoints are deemed futile, or in the scenario that all study endpoints are deemed efficacious the study will stop at this stage. If all of the study endpoints are deemed promising then the study will continue to stage 2. If there is a combination of results, the Trial Steering Committee (TSC) and IDMC will decide whether the study progresses to stage 2.

	Expected proportion	Futility threshold at stage 1	Promising result range at stage 1	Efficacy threshold at stage 1
Sensitivity	65%	<46.5%	46.5% to 63.1%	>63.1%
Specificity	95%	<92.0%	92.0% to 94.9%	>94.9%
Resectability	40%	<21.0%	21.0% to 38.1%	>38.1%

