9.3 STUDY TIMEPOINTS

There will be three timepoints for blood collection: at baseline (T0), 6 months +/- 2 weeks post-baseline (T1), and 12 months +/- 2 weeks from baseline (T2). For each study timepoint, the Avantect test will be conducted. For samples collected from participants assigned to the intervention arm, the Avantect test will be assessed as soon as possible within 14 business days of receipt of samples in the analysing laboratory at ClearNote Health. Those with positive test results (test result = Avantect “detected”) in the intervention arm will undergo diagnostic pancreas imaging. Samples collected from participants assigned to the Control arm will be stored for potential future Avantect testing or future research.

The study design comprises a pilot and two study stages:

- Stage 1 Analysis will be carried out 6 months after the T1 visit for 3,200 participants in the intervention arm. Only participants followed up for a minimum of 6 months after the T1 visit in the intervention arm will be included in this analysis.
- Stage 2 Analysis will be carried out after 3-year follow-up data has been collected for all 15,000 participants.

In addition, during the study annual readouts will be provided to the data monitoring committee to monitor study progress and inform on decisions to continue or stop the study.

The diagnostic performance of the Avantect test results will be summarised according to the pancreatic cancer diagnoses collected by the point of analysis. The stage shift, and resection rate of pancreatic cancer will be summarised by arm. For this purpose, a positive test at any timepoint will be considered a ‘positive prediction’ e.g., if a participant has a negative result at T0, but a positive result at T1, their overall prediction will be considered as at-risk of pancreatic cancer.

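### The >99% power for specificity holds only if specificity over up to three tests is 95%, which the protocol neither states nor supports

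*Protocol*

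**What the plan says.** The endpoint is cumulative and concerns pancreatic cancer (PC). Section 2.2 takes this count as its numerator: "number of individuals in the intervention arm with no Avantect “detected” test results, at least one Avantect “not detected” test result and no diagnosis". Section 9.2 repeats the rule for Stage 1: "All individuals with one or more Avantect “detected” test results will be included as positive predictions". Section 9.3 plans a test at T0, 6 months and 12 months ("For each study timepoint, the Avantect test will be conducted") and states that "For this purpose, a positive test at any timepoint will be considered a" positive prediction.

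The planning figure is a single number. Section 9.2 takes 65% sensitivity and 95% specificity as conservative values for the Avantect test and continues: "with an anticipated test sensitivity of 65% and specificity of 95%, this leads to the following confusion matrix in the intervention per protocol group". The matrix has 6,877 true negatives and 362 false positives. From it the protocol concludes that "more than 99% power is achieved to rule out a specificity lower than 92" per cent. The Stage 1 table in sections 9.2 and 9.4 lists 95% as the expected specificity, with futility below 92.0% and efficacy above 94.9%. Section 9.4 derives the expected PPV from the same matrix.

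The only independent validation result in the document is in section 1.2: "The performance of PC detection was at 66.7% sensitivity and 96.9% specificity", from 2,048 non-cancers and 102 cancers, with no repeat testing described. In the sample-size section, the reason given for three draws is missing results: "To reduce the number of participants where no test results are available, three collection time points are included". The effect of three draws on false positives is not mentioned.

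**The concern.** A participant tested up to three times has up to three chances of a false positive, so any-of-three specificity cannot exceed the lowest single-round specificity. It equals the per-test value only if the same people are falsely positive every time.

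The planning pair of 65% and 95% sits just below the validated pair of 66.7% and 96.9%, which suggests per-test values rounded down. Sensitivity points the same way: any-of-three scoring can only raise it, so a cumulative planning value below the validated one would be unexpected.

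Section 9.2 requires all three co-primaries to succeed. If the true any-of-three specificity is near or below 92%, the trial fails on this endpoint even though the test performs as validated. The same figure drives the expected number of false positives, the PPV and the Stage 1 classification.

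**Working it through.** **Inputs from the protocol.** Intervention arm 7,500; 2.5% without any result; PC prevalence 1%; planning specificity 95%; null 92%; final one-sided p-value 0.03 (section 9.4); validation specificity 96.9% (section 1.2).

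**Reproducing the plan.** 7,500 × 0.975 = 7,312; 1% of that is 73 cases, leaving 7,239 non-cases. 7,239 × 0.95 = 6,877, so there are 362 false positives. The cut-off by normal approximation is 0.92 + 1.881 × √(0.92 × 0.08 / 7,239) = 0.926; the exact binomial cut-off is 6,704/7,239 = 92.6%. If true participant-level specificity is 95%, power exceeds 99.9%. The stated figure reproduces. Sections 9.2 and 9.4 give differing alpha levels (0.05, 0.025, 0.03 and a 98.5% interval); these do not change the result.

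**Any-of-three specificity.** With independent errors it is s³: 0.969³ = 91.0% and 0.95³ = 85.7%. Between independence and perfect repetition I used an equicorrelated latent-normal model, E[Φ((t − √ρ·x)/√(1 − ρ))³], where t = Φ⁻¹(s) and x is standard normal. The protocol gives no correlation, so ρ is an assumption and is shown as a range. Three valid tests per person are assumed. Power is exact binomial at one-sided 0.03.

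| Per-test specificity | ρ | Any-of-three specificity | False positives of 7,239 | Power against 92% |
|---|---|---|---|---|
| 96.9% | 0 | 90.99% | 653 | about 0 |
| 96.9% | 0.5 | 92.35% | 554 | 21% |
| 96.9% | 0.6 | 92.80% | 521 | 75% |
| 96.9% | 0.7 | 93.35% | 482 | 99% |
| 96.9% | 0.9 | 94.89% | 370 | >99% |
| 95% | 0 | 85.74% | 1,032 | about 0 |
| 95% | 0.5 | 88.16% | 857 | about 0 |
| 95% | 0.8 | 90.74% | 670 | about 0 |
| 95% | 0.90 | 92.05% | 576 | 4% |
| 95% | 0.95 | 92.95% | 511 | 87% |

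Merely to reach 92% takes ρ = 0.41 from 96.9% and ρ = 0.90 from 95%. Latent correlations are larger than correlations between the yes/no results: on a beta-binomial intraclass scale the same break-even points are about 0.13 and 0.61.

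**Fewer tests.** With two independent tests, 0.969² = 93.9% (power >99%) and 0.95² = 90.25% (power about 0).

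**Stage 1.** 3,200 × 0.99 = 3,168 non-cases. At 96.9% per test, the chance of observing less than 92.0%, and so of being classed futile, is about 98% with independent errors and 23% at ρ = 0.5.

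**PPV.** The plan expects 48/410 = 11.7%. Under independence, with both error rates accumulating:

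- From 66.7%/96.9%: sensitivity is 1 − 0.333³ = 96.3%, or about 70 of 73, so PPV is 70/(70 + 653) = 9.7%.
- From 65%/95%: sensitivity is 1 − 0.35³ = 95.7%, again about 70, so PPV is 70/(70 + 1,032) = 6.4%.

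**The case against.** The protocol never calls 95% a per-test figure. Section 2.2 uses the phrase specificity of the Avantect test for the cumulative endpoint itself. Section 9.2 applies 95% to participants, and the Stage 1 table lists it as expected for that endpoint. It is described as conservative: 5.0% false positives against 3.1% in validation, a margin that could have been meant as an allowance for repeat testing. All of this stands, so the per-test reading is an inference. The sensitivity argument supports that inference but does not prove it.

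Independence is an extreme case for one classifier applied to the same person within 12 months. Positive correlation is likely, and from 96.9% a latent correlation of about 0.7 preserves the power. Three valid tests is also a ceiling: section 6.1 expects about 4% of samples to fail, and some people stop testing early. Both points soften the effect. Neither replaces a stated assumption.

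Four stronger readings are tempting but unsupported:

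- A reader might infer that the >99% power is miscalculated. It is arithmetically right if 95% is the any-of-three value.
- A reader might infer that PPV falls below its 5% null. Holding true positives at 48 against 1,032 false positives does give 4.4%, but the any-positive rule raises sensitivity as well, and the consistent figure is 6.4%.
- A reader might infer that a futile specificity result would stop the trial at Stage 1. Section 9.2 stops for futility only if all endpoints are futile and sends mixed results to the TSC and IDMC.
- A reader might infer that the 92% criterion belongs on per-test specificity. The documents do not give the unit behind the FDA discussion, and that change would pair a per-test specificity with an any-of-three sensitivity.

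**Conclusion.** The concern holds as a gap between the endpoint and its planning value. The power, the 362 false positives, the PPV and the Stage 1 specificity bounds are valid only if specificity over up to three tests is 95%. The protocol does not say so, gives no within-person correlation, and cites no repeat-testing data.

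The consequence ranges from none to decisive. From the validated 96.9% per test, power runs from about 0 (independent errors) through 21% (ρ = 0.5) to 99% or more (ρ of 0.7 and above). If 95% is per test, near-perfect repetition of errors is needed. A test performing as validated could therefore fail a required co-primary through repeat testing alone, although the documents do not show that it will. These figures assume three valid tests per person and a latent-normal correlation model. The protocol itself fixes the endpoint, null, bounds and power, so this is not a detail left to the SAP.

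**What to change.** Keep the any-of-three endpoint, which matches the any-positive decision rule and the sensitivity co-primary. Then:

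1. State whether the 95% planning value and the 92% criterion are per test or per participant over three tests.
2. Restate expected specificity, the confusion matrix, PPV (with sensitivity accumulating under the same rule), the Stage 1 specificity bounds and power on the any-of-three scale. Do this over a stated range of within-person correlation and of valid tests per person. For orientation, independent errors would require 0.95^(1/3) = 98.3% per test to give 95% over three tests.
3. Report per-test specificity, with standard errors clustered by participant, as a supporting analysis.

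This should be done before the Stage 1 bounds are applied. The cost is protocol wording and recalculation, and a less favourable stated power for specificity. No new data are needed.
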